3.1.2 Study Design

This study will include 4 cohorts of 14 ZIKV and DENV-naïve female and male subjects, 18 - 40 years of age (total: up to 56 subjects). Within each cohort, 10 subjects will receive ZIKV and 4 subjects will receive a placebo on Study Day 0. Cohorts 1 and 2 (Dose = 10^2 PFU) will be enrolled first and will enroll only women. Cohorts 3 and 4 (Dose = 10^2 PFU) will enroll men.

3.1.2.1 Initial Enrollment of Each Cohort

For each cohort, only the first 7 subjects (5 ZIKV recipients; 2 placebo recipients) will be enrolled until all 7 subjects have completed Study Day 28 and the criteria listed in Section 3.1.2.2 have been met. If the criteria to enroll the remaining 7 subjects from a dose cohort are met, enrollment will proceed. For cohorts 3 and 4, mosquito-feeding will be performed on a subset of enrolled volunteers. A total of 7 volunteers (randomized 5:2 ZIKV:placebo) from cohort 3 and 7 volunteers (randomized 5:2 ZIKV:placebo) from cohort 4 will undergo mosquito-feeding.

3.1.2.2 Enrollment of Remaining 7 Subjects in a Dose Cohort

The remaining 7 subjects in a dose cohort may be enrolled if the following criteria are met:

1. Halting criteria have not been met **and**
2. ≥ 4 subjects in a cohort have detectable infectious virus with a mean peak titer $\geq 1.0 \log_{10}$ PFU/mL **and**
3. ≥ 4 subjects in a cohort have detectable infectious virus for at least 2 days

3.1.3 Sample Size and Placebo Ratio Primary Study

Fourteen subjects (10 ZIKV and 4 placebo recipients) will be enrolled into each dose cohort. This sample size was chosen based on our experience in developing the DENV-2 CHIM (CIR286, clinical trials.gov NCT01931176, [47]) and the DENV-3 CHIM (CIR304, clinical trials.gov NCT02684383).

Ten subjects are chosen to receive each ZIKV strain at each dose for the following reasons:

- A sample size of 10 ZIKV recipients and 4 placebo recipients in each cohort will be able to detect a statistically significant difference ($\alpha = 0.05$) in recovery of infectious ZIKV from the blood between the 10 ZIKV recipients and 4 placebo recipients at a power of 0.99 with $\geq 80\%$ of ZIKV-inoculated subjects having detectable ZIKV viremia and none of the placebo recipients having detectable viremia.

- A sample size of 10 ZIKV recipients and 4 placebo recipients in each cohort will be able to detect a statistically significant difference ($\alpha = 0.05$) in any clinical sign between the 2 groups at a power of 0.71 if the clinical sign occurs in $\geq 80\%$ of ZIKV recipients and occurs in ≤ 1 placebo recipients. We have included placebo-recipients so that we can determine if common AEs are ZIKV-related.

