1.3.2.3 ZIKV-SJRP (Cohort 1)

ZIKV-SJRP or placebo was administered to 14 women in cohort 1 randomized 5:2 in 2 blocks of volunteers. Ten women received ZIKV-SJRP and 4 women received placebo. Adverse events following administration of ZIKV-SJRP or placebo are shown in Table 4. ZIKV-like rash was observed in 9/10 volunteers who received ZIKV-SJRP and was the most common adverse event related to ZIKV-administration. Non-purulent conjunctivitis occurred in 50% of ZIKV-SJRP recipients, arthralgia in 70% and myalgia in 50%. Fever was not observed nor were any signs or symptoms consistent with GBS.

ZIKV-SJRP was recovered from 100% of those who received the virus. Both infectious virus and virus detected by PCR were recovered from the serum of all 10 infected volunteers (Figure 5). The virus detected by PCR was below the cut-off for discharge from the inpatient unit at all times post-administration. Infectious virus titer peaked at day 5 in 6/10 volunteers. The mean peak titer was 46.8 PFU/mL (1.67 \log_{10} PFU/mL). Peak virus titer was below 100 PFU/mL (2 \log_{10} PFU/mL) in 8/10 volunteers and below 1,000 PFU/mL (3 \log_{10} PFU/mL) in the remaining 2 volunteers. Infectious ZIKV-SJRP was found infrequently in CVS, saliva, and urine (Table 5). ZIKV-SJRP was found by qPCR in urine, saliva, and CVS in 80%, 70%, and 50% of women, although the titers were low and the duration of shedding short (Table 5). ZIKV-SJRP was not recovered from any specimen taken from placebo recipients. The low peak titer following inoculation with 100 PFU of ZIKV-SJRP suggests that challenge studies may be safely performed in an outpatient setting.

Table 4: All Adverse Events Following One Dose of Cohort 1 (ZIKV-SJRP/placebo) (CIR 316)

	ZIKV-SJRP (n=10) N (%)	Placebo (n=4) N (%)	P value (1-sided) ¹
Local			
Erythema	1 (10.0%)	0 (0.0%)	0.7143
Tenderness	1 (10.0%)	0 (0.0%)	0.7143
Pain	0 (0.0%)	0 (0.0%)	n/a
Pruritus	0 (0.0%)	0 (0.0%)	n/a
Induration	0 (0.0%)	0 (0.0%)	n/a
Systemic			
Fever	0 (0.0%)	0 (0.0%)	n/a
Headache	9 (90.0%)	3 (75.0%)	0.9341
Zika-like Rash	9 (90.0%)	0 (0.0%)	0.0050
Neutropenia ²	1 (10.0%)	0 (0.0%)	0.7143

	ZIKV-SJRP (n=10) N (%)	Placebo (n=4) N (%)	P value (1-sided) ¹
Nonpurulent conjunctivitis	5 (50.0%)	0 (0.0%)	0.1259
Elevated ALT	0 (0.0%)	1 (25.0%)	1.0000
Myalgia	5 (50.0%)	0 (0.0%)	0.1259
Arthralgia	7 (70.0%)	0 (0.0%)	0.0350
Retro-orbital Pain	4 (40.0%)	0 (0.0%)	0.7203
Fatigue	5 (50.0%)	2 (50.0%)	0.4286
Muscle weakness	1 ³ (10.0%)	0 (0.0%)	0.7143

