3.1.6 Treatment Assignment

Subjects will be randomly assigned to receive ZIKV or placebo in a 5:2 ratio within each cohort. Inoculation assignment will be done using a random number generator to prepare the sequence in which subjects are assigned to receive ZIKV or placebo. Subjects will be centrally randomized by the test article preparation study staff at Johns Hopkins Bloomberg School of Public Health (JHSPH) in blocks of 7. There will be 2 blocks of 7 subjects for each cohort and there will be a total of 4 cohorts enrolled. Each block of 7 will include 5 ZIKV recipients and 2 placebo recipients. As described above, each cohort will initially enroll one block of 7 subjects. The second block of 7 subjects will be enrolled if criteria in Section 3.1.2.2 are met. Subjects will be enrolled sequentially. Cohorts of both ZIKV strains may be enrolled simultaneously. Once all 7 subjects in a block have reached Study Day 90, the inoculation assignment for that block may be unblinded to all staff.

On Study Day 0, once subjects have met all eligibility criteria, study staff will assign the subjects sequential ID study numbers from a prepared list. Subjects will be considered enrolled when they are inoculated. Clinical staff will remain blinded to inoculation assignment until all subjects within a block have reached Study Day 90.

A master log of inoculation assignments will be maintained in a record separate from other study records. This log will be maintained in a locked room with limited access. A sealed envelope containing a copy of the inoculation assignment will also be kept by the Data and Safety Monitoring Board (DSMB) Executive Secretary.

The subjects will be informed of their inoculation assignment after their block has completed Study Day 90.

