The study is powered to detect a difference in the occurrence of virus in blood, urine, cervico-vaginal secretions, or saliva following administration of one of 2 ZIKV at different doses, compared with placebo recipients. A sample size of 10 ZIKV recipients and 4 placebo recipients will be able to detect a statistically significant difference ($\alpha = 0.05$) in recovery of infectious ZIKV from the blood between the ZIKV and placebo groups at a power of 0.99 with $\geq 80\%$ of ZIKV-inoculated subjects having detectable ZIKV viremia and 0 placebo recipients having detectable ZIKV in blood and body secretions. The detection of ZIKV by RT-PCR and by virus culture from blood, urine, cervico-vaginal fluids, semen and saliva in recipients of each ZIKV strain will be compared to placebo recipients. In addition, the magnitude and duration of ZIKV presence in blood, urine, cervico-vaginal secretions, semen and saliva will be compared to one another at each dosing level. The effect of dose escalation on the presence of virus in blood, urine, saliva, cervico-vaginal secretions and semen will also be evaluated. Multiple comparisons analysis will be used to compare the magnitude and duration of virus presence at each dose level of each candidate ZIKV and placebo recipients.

Measuring the transmissibility of ZIKV-SJRP and ZIKV-Nicaragua from infected volunteers to mosquitoes is an exploratory endpoint. Following feeding on volunteers, mosquitoes will be returned to the NIH for analysis (Section 6.7). The heads and thoraces of the mosquitoes will be examined for ZIKV antigen. If antigen is detected in the head of the mosquitoes, it will be assumed that the virus escaped the mid-gut barrier and is present in the salivary glands.

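### Stated powers of 0.99 (viremia) and 0.71 (clinical sign) for 10 versus 4 name no test or side and are not reached with Fisher's exact test; the power claim for other fluids has no figures behind it

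*Combined protocol and SAP*

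**What the plan says.** Section 3.1.3 sets the cohort size: "Fourteen subjects (10 ZIKV and 4 placebo recipients) will be enrolled into each dose cohort". It then makes two power statements at alpha 0.05.

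- **Viremia:** a difference can be detected "in recovery of infectious ZIKV from the blood between the 10 ZIKV recipients and 4 placebo recipients at a power of 0.99", assuming at least 80% viremic on ZIKV and none on placebo.
- **Clinical sign:** a difference can be detected "in any clinical sign between the 2 groups at a power of 0.71 if the clinical sign occurs in" at least 80% of ZIKV recipients and at most one placebo recipient.

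Section 9.2 repeats the 0.99 for blood, but not the 0.71, and opens that paragraph more broadly: "The study is powered to detect a difference in the occurrence of virus in blood, urine, cervico-vaginal secretions, or saliva". No rate or power follows for any fluid other than blood.

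Neither section names the test or side behind the power figures. For proportions, Section 9.2 lists chi-square tests, Fisher's exact test and logistic regression, to be chosen as suits the data. The comparisons already reported in Tables 4 and 6 carry the column heading "P value (1-sided)".

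**The concern.** With four placebo subjects the outcome is very discrete, and large-sample power formulas can be far from what a test that holds its level delivers. A power of 0.71 for a sign means little if the trial can observe the rates it planned for and still miss significance.

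The sign comparison has a stated purpose. Section 3.1.3 gives attribution of common adverse events as the reason for having placebo recipients, and Section 2.1 makes signs and symptoms versus placebo part of the primary assessment. A reader who takes 0.71 at face value would give a null comparison more weight than it can bear. Shedding in urine, secretions and saliva is also under the primary objectives, so an unquantified power claim there may mislead in the same way.

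**Working it through.** **Inputs.** n = 10 and 4, alpha 0.05, rates 0.80 versus 0 and 0.80 versus 1/4 = 0.25 (Section 3.1.3; 25% is my reading of at most one of four). Fluid rates are from Section 1.3.2.3, Table 5 and Table 7.

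**1. Reproducing the plan's figures (one-sided z, critical value 1.645).**

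- Viremia, pooled: mean rate 8/14; null SE = sqrt(0.5714 × 0.4286 × (1/10 + 1/4)) = 0.2928; alternative SE = sqrt(0.8 × 0.2/10) = 0.1265. (0.80 − 1.645 × 0.2928)/0.1265 = 2.517, so power is **0.994**.
- Sign, unpooled: SE = sqrt(0.16/10 + 0.1875/4) = 0.2507. 0.55/0.2507 − 1.645 = 0.549, so power is **0.708**.
- The pooled formula gives 0.631 for the sign; the unpooled formula gives more than 0.999 for viremia. Two-sided versions give 0.963 (pooled, viremia) and 0.592 (unpooled, sign).

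So the figures come from one-sided, uncorrected approximations. Enumerating every 10 × 4 outcome, the maximum type I error of the one-sided tests at nominal 0.05 is 0.08 for pooled z and 0.154 for unpooled z. The stated power is not power at alpha 0.05.

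**2. Which test the documents use.** One-sided Fisher with x of 10 versus 0 of 4 is C(10,x)/C(14,x).

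- Rash, 9/10: 10/2002 = 0.0050
- Arthralgia, 7/10: 120/3432 = 0.0350
- Myalgia, 5/10: 252/2002 = 0.1259

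All three match Table 4. Not every entry there does, so I rely on these three.

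**3. Fisher rejection regions.**

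- Placebo 0/4: 7/10 gives 0.0350 one-sided. Two-sided adds the equally likely opposite table, for 0.0699. 8/10 gives 45/3003 = 0.0150 either way. The cut-off is at least 7 one-sided and at least 8 two-sided.
- Placebo 1/4: 8/10 gives (45 × 4 + 10)/2002 = **0.095**, one- or two-sided. 9/10 gives (10 × 4 + 1)/1001 = 0.041. The cut-off is at least 9.
- Placebo 2/4: even 10/10 gives 6/91 = 0.066, so significance in favour of ZIKV is out of reach.

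**4. Exact power, X ~ Bin(10, 0.8).** P(X≥7) = 0.879, P(X≥8) = 0.678, P(X≥9) = 0.376.

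- Viremia: 0.879 one-sided, 0.678 two-sided. At a true rate of 90%: 0.987 and 0.930.
- Sign: P(0 of 4 on placebo) = 0.75⁴ = 0.3164; P(1 of 4) = 4 × 0.25 × 0.75³ = 0.4219. One-sided: 0.3164 × 0.879 + 0.4219 × 0.376 = **0.437**. Two-sided: 0.3164 × 0.678 + 0.4219 × 0.376 = **0.373**.
- Fixing the placebo result at exactly 1 of 4 gives 0.376 either way. A lower true placebo rate of 20% gives 0.514 one-sided and 0.432 two-sided; 10% gives 0.686 and 0.554. All are below 0.71.

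| Comparison | Stated | Fisher one-sided | Fisher two-sided |
|---|---|---|---|
| Viremia, 80% vs 0 | 0.99 | 0.88 | 0.68 |
| Sign, 80% vs 25% | 0.71 | 0.44 | 0.37 |

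**5. Other fluids, Fisher power versus none on placebo, at the observed rates.**

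| Rate | Where observed | One-sided | Two-sided |
|---|---|---|---|
| 10% | SJRP culture: CVS, urine | <0.001 | <0.001 |
| 20% | Nicaragua culture: urine | 0.001 | <0.001 |
| 30% | SJRP culture: saliva | 0.011 | 0.002 |
| 50% | SJRP PCR: CVS | 0.172 | 0.055 |
| 70% | SJRP PCR: saliva | 0.650 | 0.383 |
| 80% | SJRP PCR: urine; Nicaragua PCR: CVS, urine | 0.879 | 0.678 |
| 100% | Nicaragua saliva: culture and PCR | 1.00 | 1.00 |

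Nicaragua culture from CVS was 0%. These rates come from 10 and 5 women and are uncertain.

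**The case against.** Four points can be made for the plan.

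- **The figures are not arithmetic slips.** A reader might infer a calculation error. They reproduce with recognised formulas, so the defect is an unnamed test and side, plus an approximation unsuited to four placebo subjects. This stands.
- **Two-sided is not in the documents.** A reader might take 0.68 and 0.37 as the true powers. The plan never says two-sided and its reported p-values are one-sided, so 0.88 and 0.44 are the figures on its own convention. This stands, and both belong on the page.
- **Fisher is not the only defensible test.** Two-sided uncorrected chi-square has maximum size 0.053 here and power 0.967 and 0.487. One-sided Boschloo, an exact test the plan does not name, has size 0.045 and power 0.967 and 0.615, and gives p = 0.045 for 8/10 versus 1/4. So the planned scenario fails under Fisher, not under every valid test. This stands, but neither test reaches 0.99 or 0.71.
- **Little rides on these tests.** Section 9.2 calls the study exploratory. Cohort expansion (Section 3.1.2.2) and strain suitability (Sections 2.1 and 7.6.3) have no significance criterion, and Section 7.2.4 leaves relatedness to the investigator. A reader might infer that a non-significant sign will be declared unrelated to ZIKV; no passage says so. Serum viremia was 10/10 and 5/5, so the viremia shortfall has had little effect so far. This lowers the priority but does not make the stated power correct.

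**Conclusion.** The concern holds in limited form. At alpha 0.05, 10 versus 4 does not deliver 0.99 and 0.71 under Fisher's exact test: power is 0.88 one-sided or 0.68 two-sided for viremia at 80% versus 0, and 0.44 or 0.37 for a sign at 80% versus 25%. This rests on Fisher being the operative test, on 25% as the placebo rate for signs, and on 80% as the ZIKV rate, which the plan gives as a floor. The sign figure is the material one.

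For urine, cervico-vaginal secretions and saliva, the power claim is unsupported. A reader might go further and call it false, or say these comparisons have almost no power. The documents do not bear that out across the board: power is near zero for most culture comparisons, but moderate to full for several PCR comparisons and for Nicaragua saliva by culture.

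This is a correction to stated power in an exploratory Phase 1 study. It does not undermine the expansion or suitability rules.

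**What to change.** - **Sections 3.1.3 and 9.2:** name the test and the number of sides behind each power figure, and restate exact power. With Fisher this is 0.88 (viremia) and 0.44 (sign) if one-sided, consistent with Tables 4 and 6, or 0.68 and 0.37 if two-sided. State the assumed placebo rate for signs as a percentage.
- **Section 9.2, other fluids:** limit the power claim to blood, or give an assumed rate and the resulting power for each fluid and assay. Call the low-rate comparisons descriptive, for example SJRP culture in cervico-vaginal secretions (10%), urine (10%) and saliva (30%), where one-sided power is at most 0.011.

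The cost is two paragraphs of wording and a less favourable stated power. Sample size and conduct are unchanged.

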3.1.4 Duration of Subject Participation

Subjects will be followed for approximately 26 weeks (approximately 180 days) from the time of the initial inoculation. Subjects will be screened for eligibility up to 60 days prior to inoculation on Study Day 0.

3.1.5 Estimated Duration of the Study

The entire duration of the study is approximately 52 weeks. Screening procedures should be completed within 60 days prior to receipt of the test article (except HIV testing, which will be completed within 14 days of inoculation). Enrollment will occur over a period of 4 - 8 weeks. The study will last for a total of approximately 26 weeks from the time the last subject is enrolled (inoculated).

3.1.6 Treatment Assignment

Subjects will be randomly assigned to receive ZIKV or placebo in a 5:2 ratio within each cohort. Inoculation assignment will be done using a random number generator to prepare the sequence in which subjects are assigned to receive ZIKV or placebo. Subjects will be centrally randomized by the test article preparation study staff at Johns Hopkins Bloomberg School of Public Health (JHSPH) in blocks of 7. There will be 2 blocks of 7 subjects for each cohort and there will be a total of 4 cohorts enrolled. Each block of 7 will include 5 ZIKV recipients and 2 placebo recipients. As described above, each cohort will initially enroll one block of 7 subjects. The second block of 7 subjects will be enrolled if criteria in Section 3.1.2.2 are met. Subjects will be enrolled sequentially. Cohorts of both ZIKV strains may be enrolled simultaneously. Once all 7 subjects in a block have reached Study Day 90, the inoculation assignment for that block may be unblinded to all staff.

On Study Day 0, once subjects have met all eligibility criteria, study staff will assign the subjects sequential ID study numbers from a prepared list. Subjects will be considered enrolled when they are inoculated. Clinical staff will remain blinded to inoculation assignment until all subjects within a block have reached Study Day 90.

A master log of inoculation assignments will be maintained in a record separate from other study records. This log will be maintained in a locked room with limited access. A sealed envelope containing a copy of the inoculation assignment will also be kept by the Data and Safety Monitoring Board (DSMB) Executive Secretary.

The subjects will be informed of their inoculation assignment after their block has completed Study Day 90.

3.1.7 Blinding

This study will be conducted as a double-blind study to avoid biased assessment of AEs. ZIKV or placebo will be prepared and drawn up into syringes by pharmacy/laboratory personnel who are not involved with the clinical assessment of subjects or performing research assays. Syringes are labeled according to standard operating procedures (SOPs)/recommendations. Because the

ZIKV diluent, PlasmaLyte, is used as placebo, there will be no difference in the appearance of the syringes.

The subject, investigator, and clinical staff will not know to which inoculation group the subject has been assigned. In addition, other personnel assigned to monitor the study will not know the inoculation assignment of the subject. If all volunteers within a block of 7 are able to be discharged from the inpatient unit on Study Day 9, the clinical staff will remain blinded to inoculation assignment until all subjects within a block of 7 subjects have reached Study Day 90. Once the time point for unblinding has occurred (Study Day 90 for subjects within a block), the Principal Investigator (PI) can request inoculation assignments in writing from the unblinded study staff.

If one or more subjects within a block of 7 does not meet discharge criteria by Study Day 9, those subjects must remain in the unit. To avoid undue burden on the subjects who have met discharge criteria, only those subjects who did not meet discharge criteria will remain in the unit even though this will be unblinding. If the need arises to unblind a specific subject's assignment for emergency medical management prior to all subjects within a block completing Study Day 90 post-inoculation, the PI will contact the CIR unblinded staff to obtain the inoculation assignment of the subject in question. Only that specific subject's assignment will be unblinded. The Sponsor and the DSMB Executive Secretary will be notified of the event within 2 business days. This will also be documented in the subject's study chart.

4 SELECTION AND ENROLLMENT OF SUBJECTS

Subjects must meet all eligibility criteria to be enrolled in the study. Because male-to-female sexual transmission of ZIKV is by far the most common pattern of sexual transmission, all male volunteers enrolled in the study must agree to use barrier contraception through Study Day 90 (per CDC guidance) post-enrollment. Female volunteers must use barrier contraception through Study Day 56 (per CDC guidance). Men will be enrolled to quantify the shedding of infectious ZIKV in semen. These data will better assess the risk of male-to-female transmission. Because ZIKV infection during pregnancy can be catastrophic to the fetus, female volunteers of childbearing potential will be required to use reliable methods of contraception, which include hormonal birth control (implantable, hormonal patch, NuvaRing®, oral contraception, Depo-Provera injection, etc.), IUD, or surgical sterilization (documented hysterectomy, tubal ligation or tubal coil; surgical sterilization procedures must be at least 3 months prior to inoculation) following CDC recommendations. Barrier contraception alone will not be considered a reliable method of birth control. Females who are postmenopausal (as defined as at least 1 year since last menstrual period); and females who exclusively have sex with females (and have no intention of conceiving a child during the study) are not considered to be of childbearing potential. Female volunteers on hormonal birth control must not be on medications or other agents that decrease the effectiveness of hormonal birth control.

To reduce the potential risk of transmission, ALL male subjects will be required to use barrier contraception through Study Day 90 and all female subjects will be required to use barrier contraception through Study Day 56 in accordance with CDC guidance. This includes females who exclusively have sex with females, females who are post-menopausal, and subjects who have undergone surgical sterilization.

Should a potential volunteer wish to use hormonal contraception or an IUD, study staff will refer her to a provider who can discuss the available contraception options with the subject. The study will pay for any costs of hormonal contraception not covered by insurance for the duration of the study and for the cost of placement of an IUD not covered by insurance if the subject decides she wants to enroll in the study and would like to use one of these methods of contraception.

